#### 3.0 PARTICIPANT NUMBER, COHORT CHARACTERISTICS, ELIGIBILITY, AND INVOLVEMENT

#### 3.1 Sample number and cohort characteristics

Twenty COH metastatic renal cell carcinoma patients about to undergo treatment with VEGF-TKIs will be enrolled to a single cohort at COH.

# 3.2 Eligibility

Patient MRN:		Patient Initials: (L,F,M):
3.2.1 Inclusion Criteri	a	
Participants must meet study:	the following criteria on screening	examination to be eligible to participate in the
1.	Age 18 or older	
2.	Cytologically or pathologically veri	fied diagnosis of RCC
3.	Diagnosis of RCC that is defined edition, 2010)	as metastatic by standard criteria (AJCC 7th
4. beg	•	F-TKI treatment with treatment has not yet
5.	Ability to understand and the willing	ngness to sign a written informed consent

IRB Protocol No. 16088 Version Date: 06/12/2020

6. Ability to read and write English

- \_\_\_\_\_7. Documented consent to participation to include the following study specific procedures:
  - a. Be able to provide to up to six serial stool collections at home and deliver to FedEx location that day as per standard operating procedure (Appendix A)
  - b. Have three 10-ml blood samples taken during a routine clinic visit
  - c. To not take probiotic supplements except as oriented
  - d. If randomized to the probiotic-supplemented group (the yogurt-based supplement Activia), be willing to comply with daily intake and record this intake as a component of a dietary log. The patient will be asked not to take any yogurt or yogurt-containing foods beyond this.
  - e. If randomized to the probiotic-restricted group, agree not to consume yogurt or yogurt-containing foods
    - Maintain a dietary log and stool frequency log (Appendix B)

#### 3.2.2 Exclusion Criteria

Prospective participants who meet any of the following criteria will not be eligible for admission into the study:

1.	Patients with a known intolerance to lactose or other constituents of Activia
2.	Patients with irritable bowel syndrome, Crohn's disease, or other clinically significant GI related condition that might confound the VEGF-TKI-related diarrhea endpoint
3.	Patients taking antibiotics or who plan to begin taking antibiotics.
4.	Any other condition that would, in the Investigator's judgment, contraindicate the patient's participation in the clinical study due to safety concerns of compliance with clinical study procedures (including compliance issues related to feasibility/logistics)

#### 3.2.3 Inclusion of Women and Minorities

The study is open to all patients who meet eligibility criteria, regardless of gender or ethnicity.

#### 3.3 Duration of Participation and Overview of What Is Expected From Participants

Participants will be in the trial for roughly three and a half months, initiating with informed consent procedures prior to commencing VEGF-TKIs and ending week 13 of VEGF-TKI therapy. Participants will provide five to six stool samples at home during participation, which they will then take to a local FedEx drop off location that same day. Participants will also provide three blood samples and complete a diet log and stool frequency log during participation. Half of all participants will be asked to consume vanilla yogurt twice a day during the study. The product is widely available and will be purchased by participant; reimbursement will be offered. Participants will be asked to refrain from taking/consuming other probiotics.

IRB Protocol No. 16088 Version Date: 06/12/2020

#### 4.0 STUDY ACTIVITY TABLE

# 4.1 Study Activity Table

	Screeninga Pre-tx		VEGF-TKI treatment b				
	Screening a	FIE-LX	Wk 1	Wk 2	Wk3	Wk 4	Wk 13
Informed consent C	Х						
Eligibility review d	Х						
Registration e	Х						
Participant orientation f		xf					
Research blood collection g		χg			χg		χg
Planned stool specimensh		χi		χj	χj	χj	χj
Stool specimen at onset of diarrheah			Xk				
Study log review/collection					χl		χl
Data collection m			Х		Х		Х
Dietary intervention n		χn		χn	χn	χn	χn
PHQ-9 and GAD-7 °		X					X

- a. Screening procedures are to occur prior to research sample collection with the following caveat: If the sample is collected on the same day as completion of eligibility review, the informed consent and eligibility review must precede sample collection; registration must occur that very day but may be before or after sample collection.
- b. Participants who end vascular endothelial growth factor tyrosine kinase inhibitor (VEGF-TKI) treatment prior to Week 13 will jump to the 'Week 13' assessments which will be performed within 1 week of the decision to end VEGF-TKI treatment.
- c. Informed consent to occur before any study specific screening procedures.
- d. Inclusion/exclusion criteria are found in Section 3.2. Source documentation providing investigator's confirmation that patient has met all eligibility criteria must be available prior to registration.
- e. Registration into MIDAS.
- f. Participants will receive training on completion of the diet log, stool frequency log, and stool specimen collection SOP by the clinician investigator. This education will be noted in the medical record.
- g. One sample of blood for research will be collected within 7 days before start of VEGF-TKI, at Week 3 (+/- 1 week), and at Week 13. Efforts will be made to collect the sample at the time of routine blood sample collection. Blood will be collected into 10 mL CPT vacutainer tube, inverted slowly about 8-10 times, maintained at RT and transported to pathology laboratory, who will ensure the sample is labeled with the "COH IRB #16088", the participants RPN, and time and date of collection, prior to transport to the [name] laboratory. The [name] laboratory should be notified of planned samples via email ([contact] or other designee) preferably at least a day in advance of sample collection. The sample should be brought to the [name] as soon as possible for processing to begin within 4 hours of the time of collection.
- h. All stools samples to be collected at home and dropped off the same day to a FedEx location prior to that day's FedEx pick-up, per Stool Collection SOP (Appendix A).
- i. Pre-treatment stool samples to be collected within 7 days of start of VEGF-TKI.
- j. Week 2, Week 3, Week 4, and Week 13 stool samples to be provided any day Monday to Thursday on the designated week.

IRB Protocol No. 16088 Version Date: 06/12/2020

- k. If diarrhea is not incurred, submission of stool is not required. Sample to be collected as early as possible after the onset of diarrhea such that the sample can be collected and delivered to FedEx drop off (Monday-Thursday only).
- I. Efforts will be made to review and/or collect the study log with participants on weeks 3, 6, 9, and 13 which correspond to the times when patients taking VEGF-TKI are usually seen (and assessed with CBC w/ dif and serum chemistry) after three weeks of treatment. It will not be a deviation if the visits to review/collect study logs are delayed or combined.
- m. Data will be collected and entered into eCRFs from the participant provided logs and the medical record. Data to be collected within two weeks of the end of the defined study point.
- n. If patients are randomized to the probiotic-supplemented group, they will be asked to purchase Activia vanilla yogurt. Patients will be asked to consume one 4 oz serving of Activia vanilla yogurt in the morning and one 4 oz serving of Activia vanilla yogurt in the evening beginning Week 2 and through Week 13.
- o. Symptoms of anxiety and depression will be assessed at the baseline (before start the treatment) and at the Week 13 (Section 8.0).

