# **EXPERIMENTAL DESIGN SCHEMA**

\*\*\*If randomized to dietary intervention, participant will be asked to consume one 4 oz serving of Activia vanilla yogurt in the morning and one 4 oz serving of Activia vanilla yogurt in the evening for the duration of the study.

IRB Protocol No. 16088 Version Date: 06/12/2020

 ${\rm **Within~24~hours~of~onset~of~diarrhea~following~initiation~of~VEGF-TKI,~a~stool~sample~is~to~be~provided}\\$ 

\*If a participant ends VEGF-TKI before week 13, a final sample is to be provided, and the study logs to that time point are to be collected. Study participation will end at that time.

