# 2.2 Overview and rationale of study design

Diarrhea is a significant toxicity experienced by roughly 50% of patients treated with VEGF-TKIs. Identifying a pre-treatment biomarker associated with treatment-related diarrhea may lead to the development of a pre-treatment conditioning regimen. Data from our pilot study in metastatic renal cell carcinoma (mRCC) patients undergoing VEGF-TKI therapy demonstrated a notably low abundance of Bifidobacterium spp. The primary objective of this study will be to ascertain whether or not the simple addition of Activia™ yogurt (containing Bifidobacterium lactis DN-173 010) will reduce this dysbiosis. Changing the abundance of this species, and indirectly other species in the complex microbiota population prior to initiating therapy may decrease in VEGF-TKI related diarrhea.

Twenty patients with mRCC will be recruited prior to initiating standard of care therapy with VEGF-TKIs, and will be followed for three months of therapy for specimen and data collection. Patients will be treated according to NCCN guideline recommendations for each VEGF-TKI agent. An intervention will be performed. Specifically, patients will be randomized to either a probiotic-supplemented group (Activia™) or a probiotic-restricted group using a permuted block design to ensure the 20 patients were assigned to the two groups with 1:1 ratio. Patients in the probiotic-supplemented group will be asked to consume one 4 oz serving of Activia vanilla yogurt in the evening daily for the 3 month study period and patients in the probiotic-restricted group will be asked to avoid any intake of yogurt or yogurt-containing foods for the evaluation period of the study.

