#### 5.0 CLINICAL DATA COLLECTION

#### 5.1 Participant Daily Diary

Participants will be oriented to complete the daily study log, found in Appendix B. The log will be collected and reviewed during visits to the clinic at the end of each 3-week treatment regimen (weeks 3, 6, 9 and 13 of treatment). The following information from the diary will be entered into the study specific database for analysis:

- Diarrhea, categorized per CTCAE 4.0 diarrhea grading. Please note that the patient will be instructed to consider diarrhea to be an increase in stool frequency of < 4 over baseline. This definition is consistent with the CTCAE 4.0 terminology for grade 1 diarrhea.
- Stool specimen collection dates
- Yogurt intake, or intake of yogurt-containing foods

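### The protocol gives two daily amounts and conflicting start points for the yogurt, and only footnote n places the baseline stool before the first serving

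*Combined protocol and SAP*

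**What the plan says.** **Daily amount.** Section 2.2 says that supplemented patients "will be asked to consume one 4 oz serving of Activia vanilla yogurt in the evening daily for the 3 month study period", with no morning serving. Section 3.3 says "Half of all participants will be asked to consume vanilla yogurt twice a day during the study". The Experimental Design Schema note, footnote n to the Section 4.1 table, Section 7.1, and the general pointers in Appendices B and D each name a morning and an evening serving.

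**First day.** Footnote n is the only text with an explicit start: after naming the morning serving it continues "one 4 oz serving of Activia vanilla yogurt in the evening beginning Week 2 and through Week 13". The row it annotates, "Dietary intervention", is marked at Pre-tx and at Weeks 2, 3, 4 and 13, and is blank at Week 1. The schema note asks for the morning serving and "one 4 oz serving of Activia vanilla yogurt in the evening for the duration of the study". Sections 2.2 and 7.1 give a three-month period. Section 3.3 describes participation as "initiating with informed consent procedures prior to commencing VEGF-TKIs and ending week 13 of VEGF-TKI therapy". Neither patient log prints a first day.

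**Baseline stool.** Footnote i reads "Pre-treatment stool samples to be collected within 7 days of start of VEGF-TKI". Sections 2.2 and 7.2 and Appendix A also refer this sample to the start of the VEGF-TKI. None of them mentions the first serving.

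**Primary analysis.** Section 8.1 compares the change from baseline in relative abundance of *Bifidobacterium* between two arms of 10. It does not define baseline further.

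**The concern.** The yogurt is the randomized treatment, so its amount and start should read the same wherever staff or patients look them up. The conflict over amount mainly affects how the intervention is described and reported. The conflict over the first day reaches the primary endpoint.

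A supplemented patient who follows the pre-treatment mark, or a log with no printed start, could eat yogurt before giving the pre-treatment stool. If yogurt raises *Bifidobacterium*, as the trial hypothesizes, baseline would rise in that arm only and the measured change would shrink. The bias is toward no effect, not toward a false positive.

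The study data could reveal this but not repair it. Section 5.1 enters stool collection dates and "Yogurt intake, or intake of yogurt-containing foods" in the database, and Appendix D records the date, size and time of each serving. The first log review is at Week 3, however, after the baseline has been taken, and footnote l allows reviews to be delayed or combined. A baseline sample taken after yogurt cannot be replaced.

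**Working it through.** This is mainly a comparison of texts. The arithmetic only gives its size.

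**1. The plan's own figure.** Section 8.1 states 85% power for the Mann-Whitney test with 10 per group, a probability of 0.85 and one-sided 0.05. Noether's formula gives Φ(√(12 × 0.25 × 20) × (0.85 − 0.5) − 1.645) = Φ(2.711 − 1.645) = Φ(1.066) = 85.7%. The figure reproduces, and nothing below changes it. The t-test statement gives no effect size to check.

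**2. Amount and start, side by side.**

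| Place | Servings a day | Start or period given |
|---|---|---|
| Schema note | 2 | whole study, no first day |
| Section 2.2 | 1 | 3 months, no first day |
| Section 3.3 | 2 | during the study, no first day |
| Section 4.1, table row | – | marked at Pre-tx, blank at Week 1 |
| Section 4.1, footnote n | 2 | Week 2 through Week 13 |
| Section 7.1 | 2 | 3 months, no first day |
| Appendix B log | 2 | none |
| Appendix D log | 2 | none |

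One place gives one serving and six give two. The count does not show which was intended.

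**3. Size of the amount conflict, over footnote n's own period.** Weeks 2 to 13 are 12 weeks, or 12 × 7 = 84 days. One a day: 84 × 1 = 84 servings. Two a day: 84 × 2 = 168 servings. Section 2.2 also equates three months with 13 weeks, one week more than footnote n's 12.

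**4. Size of the start conflict.** Assumptions, not stated in the documents: the VEGF-TKI starts on day 1, there is no day 0, Week 2 begins on day 8, and Pre-tx means days −7 to −1 (borrowed from the footnote i window).
- First serving on day −1: 1 + 7 = 8 days before day 8.
- First serving on day −7: 7 + 7 = 14 days before day 8.

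**5. Possible intake before the baseline stool, on the same assumptions.**
- Stool collected first: 0 days, 0 servings.
- Yogurt from day −7, stool on day 1 just before the first VEGF-TKI dose: 7 days, and 7 × 2 = 14 servings at two a day.
- Under footnote n's Week 2 start: 0.

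**6. Order of stool and yogurt.** Footnote i, Sections 2.2 and 7.2, and Appendix A fix the stool relative to the VEGF-TKI. Only footnote n fixes the yogurt relative to the VEGF-TKI. The intended order follows only by combining the two, and the pre-treatment mark on footnote n's own row points the other way.

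**The case against.** The strongest reply is that footnote n already supplies the rule. It is the only explicit first day, and the pre-treatment mark carries the footnote's letter, so a reader of the mark is sent to Week 2. The mark may have an innocent meaning: footnote n also covers buying the yogurt, and the row's marks match those of the planned-stool row exactly, so they may follow the sampling schedule rather than days of intake. Sections 2.2 and 7.1 link the three months to therapy, which suggests a start near the first VEGF-TKI dose. The logs have a date column, and patients are trained on them before treatment.

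Much of this is plausible, but the documents do not say it. The table does not limit the mark to purchase or to visits. Orientation has its own pre-treatment row, and its footnote does not mention when yogurt begins. The Section 2.2 rationale speaks of altering the flora before therapy starts, which makes an earlier start a natural reading. Dated log entries record what a patient did; they do not tell the patient when to begin.

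Three limits stand. The 7-day window is an assumption, so 14 servings is not a documented maximum. The schema figure and consent pages were not available and might show the order. The documents do not show how often early intake would occur.

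**Conclusion.** The concern holds. The conflict over daily amount, and the conflict between the table row and its own footnote over the first day, are certain from the text. It is also certain that, in the text read, only footnote n's start places the baseline stool before the first serving.

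The amounts differ twofold. The start differs by 8 to 14 days under the day-count assumptions, with 0 to 7 days of yogurt possible before the baseline stool. The effect on the primary comparison is a possible bias toward no effect, of unknown frequency and size. No loss of power is claimed. This should be fixed because it concerns the randomized intervention and the baseline of the primary endpoint.

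**What to change.** - Reconcile the schema note, Sections 2.2, 3.3 and 7.1, the Section 4.1 row and footnote n, and Appendices B and D so that all state one daily amount, one first day and one duration. Which values to adopt is for the sponsor.
- Say what the pre-treatment mark on the dietary row means, or change it to agree with the chosen first day.
- Print the first day in the Appendix B and D logs.
- State in footnote i, Section 7.2 and Appendix A that the pre-treatment stool is collected before the first yogurt serving.

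The cost is a wording amendment and revised patient instructions. No extra patients or samples are needed.

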#### 5.0 CLINICAL DATA COLLECTION

#### 5.1 Participant Daily Diary

Participants will be oriented to complete the daily study log, found in Appendix B. The log will be collected and reviewed during visits to the clinic at the end of each 3-week treatment regimen (weeks 3, 6, 9 and 13 of treatment). The following information from the diary will be entered into the study specific database for analysis:

- Diarrhea, categorized per CTCAE 4.0 diarrhea grading. Please note that the patient will be instructed to consider diarrhea to be an increase in stool frequency of < 4 over baseline. This definition is consistent with the CTCAE 4.0 terminology for grade 1 diarrhea.
- Stool specimen collection dates
- Yogurt intake, or intake of yogurt-containing foods

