Several stool collections will be performed. Stool samples will be collected prior to initiating VEGF-TKI treatment, one week after initiating therapy, two weeks after initiating therapy, three weeks after initiating therapy (i.e. after the first week off of therapy), three months (13 weeks) into VEGF-TKI therapy, and at the onset of diarrhea. A stool specimen at the onset of diarrhea would reflect changes in the bacteriome that could potentially drive onset of this symptom. Compliance with stool submission has not been an issue in our pilot study (IRB 12096). All stool samples will be collected by the participant at home and sent via overnight shipping to the laboratory at City of Hope. Participants will receive training on the sample collection process. Participants will also be asked to complete a diet log and stool frequency log that uses the CTCAE v4.0 definitions of diarrhea:

IRB Protocol No. 16088 Version Date: 06/12/2020

- Grade 1: Increase of <4 stools per day over baseline; mild increase in ostomy output compared to baseline
- Grade 2: Increase of 4 6 stools per day over baseline; moderate increase in ostomy output compared to baseline
- Grade 3: Increase of >=7 stools per day over baseline; incontinence; hospitalization indicated; severe increase in ostomy output compared to baseline; limiting self care ADL
- Grade 4: Life-threatening consequences; urgent intervention indicated
- Grade 5: Death

For purposes of the current study, we are interested in characterizing the incurrence of all grade diarrhea (e.g., grade 1-5 toxicity); however, the grade of diarrhea incurred will be specified.

From the serial stool samples, *Bifidobacterium spp*. levels and stool bacteriomic profile over time will be assessed and associations will be examined between patients who experience diarrhea and those who do not.

To explore potential confounding factors or associations of interest between the bacteriomic profile and the presence of diarrhea, data collection will include: intake of yogurt, general description of daily diet, prior anti-cancer therapies, concomitant medications during the study period, and response to VEGF-TKIs. These data will be collected from the participant's medical record or from the participant's daily log.

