#### **APPENDIX A: STOOL COLLECTION PROCEDURE**

#### STOOL COLLECTION KIT GENERAL INSTRUCTIONS

As a part of your participation in the current study, we have some specific instructions related to collection of stool. Please abide by these instructions, as they are essential for the proper conduct of the study.

Keep a "cold pack" in your freezer so that it is ready when it is needed. (We suggest putting them in your freezer when you get home).

Samples should be collected only if:

- It is a Monday, Tuesday, Wednesday or Thursday.
- They can be taken to the FedEx drop-off location before the last pick-up time.

The last pick-up time is different for different locations; it can be as early as 3:00PM.

IRB Protocol No. 16088 Version Date: 06/12/2020

Ask a study team member if you need assistance to locate a FedEx drop-off location or find the time of the last pick-up.

You are being asked to collect samples at the following times:

- Before you begin treatment with VEGF-TKI :\_\_\_\_\_\_\_
- The week after the week you started VEGF-TKI:
- Two weeks after you started VEGF-TKI:
- Three weeks after you started VEGF-TKI:
- The thirteenth week after you started treatment with VEGF-TKI:
- On the first day you have diarrhea and the sample can be collected and dropped off (see example below).

Examples of when to collect the diarrhea samples:

EXAMPLE 1: If diarrhea begins on a Saturday, wait until Monday to collect a sample and take it that day to the FedEx drop off. You do not need to still have diarrhea on Monday.

EXAMPLE 2: If diarrhea begins on Wednesday, but you cannot take the sample to the FedEx location that day on time, wait until Thursday (the day after start of diarrhea) to collect the sample and take it to the drop off location.

If you have a	ny questions about	cample collection	nlaaca call thic nu	mhari
ii vou nave ai	iiv uuestioiis about	Sample Conection.	Diease call tills flui	niber.

IRB Protocol No. 16088 Version Date: 06/12/2020

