# Example of the signature line:

• When you hand over the document to the study team, they will ask to sign and date at the bottom of each log if you agree that the information is complete and correct.

At the time of handing over the document Pa	articipant Signature:	Date 12/18/2002
---	-----------------------	------------------------

IRB Protocol No. 16088 Version Date: 06/12/2020

	_		
COMPLETED BY STUDY TEAM	Participant Initials:	Participant Research Number:	Group:
COMPLETED BY STODY TEAM	rai ticipant initiais.	Farticipant Research Number.	Group.
	•	·	•

Day and Date	General description of food I ate:	Did I eat yogurt or take probiotics?	How was my stool frequency?	Was a stool sample collected?	Medications taken	Initials of person filling information
	Eggs, toast, juice Ham sandwich, coke, potato chips	○ Yes	Seems like baseline ○1-3 stools more than baseline	○ Yes	Vítamín C, lípítor	1 For
	Steak, m ashed potatoes, wine	XNo	

○4-6 stools more than normal

○7 or more than baseline, or incontinence

	₹ No		LBC .
			○ Seems like baseline			
		○ Yes	○1-3 stools more than baseline	○ Yes		
		○ No	○4-6 stools more than normal	○ No		
			○7 or more than baseline, or incontinence			
		○ Yes	

Seems like baseline

1-3 stools more than baseline

	○ Yes		
		○ No	

○4-6 stools more than normal

○7 or more than baseline, or incontinence

	○ No		
		○ Yes	
 
○ Seems like baseline
 
○1-3 stools more than baseline
 
	○ Yes		
		○ No	○4-6 stools more than normal ○7 or more than baseline, or incontinence	○ No		
		O Vos	○ Seems like baseline	○ Yes		
		○ Yes ○ No	

○1-3 stools more than baseline

○4-6 stools more than normal

	○ No		
			○7 or more than baseline, or incontinence			
		○ Yes	

○ Seems like baseline

○1-3 stools more than baseline

	○ Yes		
		○ No	

○4-6 stools more than normal

○7 or more than baseline, or incontinence

	○ No		

IRB Protocol No. 16088

Version: 09

Version Date: 06/12/2020

Bacteriomic Profiling Associated with Vascular Endothelial Growth Factor Tyrosine Kinase Inhibitor-Induced Diarrhea
Page 30 of 35

		
 
Seems like baseline
 
			
	○ Yes	○1-3 stools more than baseline	○ Yes		
	○ No	○4-6 stools more than normal	○ No		
	0.10	○7 or more than baseline, or incontinence			
At the time of handing over the document Parti	cipant Signatu	ıre:		Date	

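### Section 5.1 tells patients that diarrhea is an increase of fewer than 4 stools; read literally this leaves out grades 2 and 3 and puts the onset stool sample at risk

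*Combined protocol and SAP*

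**What the plan says.** Section 5.1 lists what is taken from the patient's diary. The diarrhea item opens with "Diarrhea, categorized per CTCAE 4.0 diarrhea grading". It then states that "the patient will be instructed to consider diarrhea to be an increase in stool frequency of < 4 over baseline" and adds: "This definition is consistent with the CTCAE 4.0 terminology for grade 1 diarrhea".

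Section 2.2 sets out the grades. The first reads "Grade 1: Increase of <4 stools per day over baseline", grade 2 is an increase of 4 to 6, and the third begins "Grade 3: Increase of >=7 stools per day over baseline; incontinence". The same section gives the scope: "we are interested in characterizing the incurrence of all grade diarrhea", meaning grades 1 to 5. Section 8.1, secondary objective 1, compares the all-grade rate between arms and also the grade 3/4 rate.

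The Appendix B log asks about stool frequency each day. It offers a no-change box and boxes for 1-3 more, 4-6 more, and 7 or more (or incontinence). The middle one is worded "4-6 stools more than normal", while the others refer to baseline.

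Appendix A tells the patient when to send the extra stool sample: "On the first day you have diarrhea and the sample can be collected and dropped off".

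**The concern.** A definition that consists only of an upper limit says what diarrhea must not exceed. An increase of 4 or more stools is worse diarrhea under Section 2.2, but under the sentence in Section 5.1 it is not diarrhea at all. The instruction given to patients therefore conflicts with the all-grade scope of the study.

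It matters because the patient, not the staff, decides at home when diarrhea has begun and when to send the onset sample. Section 2.2 wants that sample because it may show the bacterial changes that drive the symptom. If it is not taken near onset, it cannot be replaced.

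**Working it through.** **Step 1: the plan's own figure.** The only number tied to the diarrhea endpoint is the power in Section 8.1: one-sided Fisher exact test at 0.05, 10 patients per arm, rates 0.200 and 0.800. Exact power is the sum over all 11 × 11 outcomes (a, b) of Bin(a; 10, 0.2) × Bin(b; 10, 0.8), counting those with one-sided Fisher p ≤ 0.05. The result is 0.8054, or 80.5%, against 80% stated. The figure reproduces. Aligning the wording with the all-grade definition leaves the planning rates, and so the power, as they are.

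**Step 2: the definitions side by side.** Each change from baseline in daily stools is classified under the Section 5.1 sentence, the Section 2.2 grades and the Appendix B boxes.

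| Change in stools | Section 5.1, literal | Section 2.2 | Appendix B box |
|---|---|---|---|
| 0 | Not an increase | No diarrhea | No change |
| +1 to +3 | Diarrhea | Grade 1 | 1-3 |
| +4 to +6 | Not diarrhea | Grade 2 | 4-6 |
| +7 or more | Not diarrhea | Grade 3 | 7 or more |

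The first two rows agree. The last two conflict: Sections 2.2 and 8.1 count these days and the literal instruction does not.

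**Step 3: where the conflict has an effect.**

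- *Graded endpoint.* The log asks for a frequency box, not for a yes or no on diarrhea. Grades 1 to 3 by stool count can be read from the boxes whatever the patient believes diarrhea to be.
- *Onset sample.* Appendix A uses the word without defining it, and the log does not say which boxes count as diarrhea. Section 5.1 is therefore the only definition that the protocol says patients will be given.

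**Step 4: whether a missed sample can be recovered.** The design schema asks for the onset sample within 24 hours, and Section 7.2 asks for it as early as feasible. Logs are reviewed at about weeks 3, 6, 9 and 13. Footnote l to the table in Section 4.1 allows those reviews to be delayed or combined. Scheduled reviews are thus 3 to 4 weeks apart (6 − 3 = 3, 9 − 6 = 3, 13 − 9 = 4), so a tick in the 4-6 box may come to light long after the sample was due.

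**The case against.** The best defense is that the sentence is only clumsy. It sits beside a reference to CTCAE grading and to grade 1, so it reads naturally as an entry threshold: even a small increase counts. The limit of 4 appears in neither patient appendix. To miss the sample, a patient would have to go straight to 4 or more extra stools, with no earlier day at +1 to +3, and then decide that this is not diarrhea although the daily form has boxes for it. Section 8.1 names no specific test for the onset sample.

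Much of this stands. The intended meaning is probably as described, and the route to harm is narrow. But the protocol states that patients will be told this rule, and the rule as stated is wrong for grades 2 and 3.

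Three stronger readings are tempting, and the documents do not support them:

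- *A reader might infer that no change also counts as diarrhea, since 0 is below 4.* The sentence requires an increase, and the log has its own no-change box. What Section 5.1 lacks is only the explicit lower limit of 1 that the log uses.
- *A reader might infer that the split into patients with and without diarrhea, used in secondary objectives 1 to 3, rests on this wording.* The diary item is graded by CTCAE, and the log boxes supply that split.
- *A reader might take the grade 3/4 share in Table 1 as the share of diarrhea missed.* Weighted by N, that share is 4.9 / 51.4 = 9.5%. But Table 1 counts each patient once, since the two grade columns add to the overall rate in every agent row (41 + 2 = 43, 52 + 9 = 61, 48 + 4 = 52). The diary rule works by day. A patient who reaches grade 3 may have had days at +1 to +3 first and would then meet even the literal rule. The 9.5% measures neither missed patients nor missed samples.

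**Conclusion.** The point holds in a limited form. Section 5.1 gives the upper limit of grade 1 as the definition of diarrhea and so contradicts the all-grade scope of Sections 2.2 and 8.1. Grading from the log survives, and no sample size or power figure changes.

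What remains is mainly a risk to the onset stool sample in patients whose first change is 4 or more stools. This assumes that the training repeats the sentence as written and that the patient takes it literally. The documents give no rate for such an abrupt onset, so the number of samples at risk cannot be estimated. With 20 patients in all, even a few lost samples would thin this part of the data. The mix of *normal* and *baseline* in the log is an editorial slip, and nothing shows that it would misclassify anyone.

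**What to change.** Reconcile Section 5.1 and the patient training with Section 2.2 and Appendix B:

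- Define diarrhea, for both the endpoint and the onset-sample trigger, as any increase over baseline that meets CTCAE v4.0 grade 1 or higher.
- Say that in the log this means any box other than the no-change box, including incontinence.
- Say that the ostomy-output criteria and the grade 4 and 5 criteria of Section 2.2 also count, since the log boxes do not show them.
- Put the same definition beside the onset-sample instruction in Appendix A, where the patient will use it.
- Replace *normal* with *baseline* in the 4-6 box.

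The cost is a reworded sentence in Section 5.1, a matching line in the training and in Appendix A, and one word in the log. No analysis, sample size or visit changes.
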